Assistant Professor of Clinical Medicine
Division of Hematology and Oncology
University of Cincinnati Cancer Institute
[name]
[name]
[name]
[contact]
E-mail: [contact]

**Phase II Trial of Concurrent Nivolumab in Urothelial Bladder Cancer with
Radiation Therapy in Localized /Locally Advanced Disease for Chemotherapy
Ineligible Patients [NUTRA]**

Table of Contents

Synopsis.....	6
1.0 Background and Rationale.....	7
2.0 Study Design.....	12
3.0 Study Population.....	18
4.0 Study Assessments.....	21
5.0 Adverse Events Reporting.....	26
6.0 Correlative Studies.....	33
7.0 Treatment Plan, Modifications and Concomitant Therapy.....	36
8.0 Statistical Considerations.....	43
9.0 Ethical Aspects.....	47
10.0 Study Documentation.....	49
11.0 References.....	52
12.0 Data and Safety Monitoring.....	53
13.0 Appendices.....	55

SYNOPSIS

Phase II Trial of Concurrent Nivolumab in Urothelial Bladder Cancer with Radiation Therapy in Localized/Locally Advanced Disease for Chemotherapy Ineligible Patients [NUTRA]

- Primary Objective:**

To compare the 12-month rate of progression-free (PFS) survival achieved with the combination of nivolumab, a programmed death (PD-1) inhibitor, and radiation therapy in localized/locally advanced urothelial cancer patients, who are ineligible for chemotherapy, to a historical control reference rate.

- Secondary Objectives:**

- 1) To assess the toxicity of concurrent nivolumab and radiation therapy in urothelial cancer.
- 2) To determine overall response rate (ORR).
- 3) To determine metastasis-free survival (MFS).
- 4) To determine overall survival (OS).
- 5) To evaluate the quality of life and bladder functioning during and after the therapy.
- 6) To explore the relationships of PD-1 expression, PDL-1 expression, and the Th1/Th2 cytokine ratio to clinical outcomes (response, PFS, MFS, and OS).

- Treatment Plan:**

- Nivolumab will be administered at a dose of 240 mg IV every 2 weeks for a maximum of 14 doses or 6 months duration.
- Radiation Therapy (RT) needs to be started within +/- 3 days of nivolumab administration. RT would be administered at a total dose of 64 Gy in 32 fractions over a 6-8 week period in all patients.

- Study Assessments:**

Prestudy evaluation, CT/MRI scan, cystoscopy and biopsy, and archival tissue. Clinical and lab evaluation on day of nivolumab therapy. QOL assessment at the 15 time points listed in the header of the Study Calendar in Section 2.3.

- Statistical Design:**

Sample size based on an assumed 12 month PFS rate of 50% on RT alone currently and a hypothesized rate of 75% for Nivolumab + RT study patients. A total of 34 patients are to

be accrued to get 30 evaluable for PFS. Evaluable for PFS and toxicity evaluable have the same definition (in Section 4.7).

1.0 BACKGROUND AND RATIONALE

1.1 Study Objectives

The objectives of this study are as follows:

- Primary Objective:

To compare the 12-month rate of progression-free survival (PFS) achieved with the combination of nivolumab, a programmed death (PD-1) inhibitor, and radiation therapy in localized/locally advanced urothelial cancer patients, who are chemotherapy ineligible, to a historical control reference 12-month PFS rate.

- Secondary Objectives:

- 1) To assess the toxicity of concurrent nivolumab and radiation therapy in urothelial cancer.
- 2) To determine overall response rate (ORR).
- 3) To determine metastasis-free survival (MFS).
- 4) To determine overall survival (OS).
- 5) To evaluate the quality of life and bladder functioning during and after the therapy.
- 6) To explore the relationships of PD-1 expression, PDL-1 expression, and the Th1/Th2 cytokine ratio to clinical outcomes (response, PFS, MFS, and OS).

1.2 Background

The standard management of localized urothelial cancer of bladder consists of neoadjuvant chemotherapy followed by radical cystectomy [1]. If patients wish to pursue a bladder sparing procedure then regimens of either 5FU and mitomycin, or cisplatin concurrently with radiation therapy (RT) are accepted therapeutic approaches [2]. However, these regimens are not feasible in a subset of bladder cancer patients who are ineligible for chemotherapy. Bladder cancer is a disease of the elderly and the incidence increases with increasing age. The median age of incidence of bladder cancer is 73 years and 9 of 10 cases occur in patients over the age of 55 years. In addition, the bladder cancer population has a very high rate of associated comorbidities such as renal dysfunction, cardiac and vascular disease and neuropathy which are frequently deterrents to administering chemotherapy. In

some series the patients who are not candidates for cisplatin based therapy due to comorbidities range up to about 40-50% of the patients presenting with localized disease. The morbidity of bladder cancer is frequently significant, with hematuria, urinary obstruction and renal dysfunction being the common and recurring complaints. Cisplatin based therapy concurrently with RT, has demonstrated results comparable to the surgical series; however, the toxicity rates are significant and about 40% of the patients are not candidates for chemotherapy [3,4]. A concurrent regimen of 5FU and mitomycin with RT [5] showed improved outcomes when compared to RT alone; however, the severe toxicity rates of 36% are a definite deterrent. We have reported on a case series of 13 patients receiving concurrent capecitabine and RT in localized bladder cancer, in whom we observed reasonable palliation and response rates [6]. 11 of 13 evaluable patients demonstrated a response and at a median follow up of 10 months only 3 had relapsed. The most common overall toxicities were fatigue (43%), diarrhea (Grade 2, 14% and Grade 3, 29%), and dehydration (43%), with no Grade 4 or 5 toxicities. The therapy options for treatment of symptomatic bladder cancer in patients who are ineligible for chemotherapy demonstrate suboptimal efficacy and hence there is an unmet need to improve the therapeutic outcomes within this patient population.

1.3 Nivolumab and Radiation Therapy (RT)

Nivolumab is a programmed death (PD) 1 inhibitor that has demonstrated safety and efficacy in multiple human malignancies and is currently approved by the FDA for the indications of metastatic melanoma, lung cancer, and renal cancer. A single arm phase II clinical trial in metastatic and post chemotherapy urothelial cancer population was completed and results were recently reported. The study showed a 19.6% (53 of 270 patients) overall response rate and a 25% response rate in patients with PDL-1 expression $\geq 1\%$. Some remissions are durable and follow up is continued. This data led to FDA approval of nivolumab in metastatic urothelial cancer post platinum based chemotherapy [7].

Preclinical synergy has been noted between nivolumab and RT in urothelial cancer. In fact the inflammation induced by the RT is likely to increase PD-1 expression in the cancer and will likely enhance efficacy. RT has shown the following effects in urothelial carcinoma: 1) increased CD8 cell function and increased cytokine release, 2) abscopal response in metastatic sites not being treated within the RT field, 3) the RT has been known to release tumor antigens and can convert the tumor into an *in situ* tumor vaccine, and 4) complementary and potentially synergistic effects in combination with immune checkpoint

inhibitors. In summary, association with proinflammatory signals that trigger the innate immune system to activate tumor-specific T cells, radiation's effects on the tumor microenvironment also enhance infiltration of activated T cells and enable overcoming some of the barriers to tumor rejection [8-11].

In the US, nivolumab has been approved for the treatment of patients with unresectable or metastatic melanoma and disease progression following ipilimumab and, if BRAF V600 mutation positive, a BRAF inhibitor. It has also been approved for use in patients with advanced (metastatic) squamous non-small cell lung cancer (NSCLC) with progression on or after platinum-based chemotherapy. Nivolumab was recently approved for metastatic urothelial cancer for patients with disease progression after platinum based chemotherapy.

Nivolumab monotherapy has been extensively studied in a number of tumor types including non-small cell lung cancer, melanoma, renal cancer, and head and neck cancer with body weight normalized dosing (mg/kg) [12]. Across the various tumor types in the Bristol-Myers Squibb (BMS) clinical program, nivolumab has been shown to be safe and well tolerated up to a dose level of 10 mg/kg, and the relationship between nivolumab exposure produced by 3 mg/kg and efficacy has been found to be unchanged at different dose levels. Taken together, the PK, safety, and efficacy data indicate that the safety and efficacy profile of 240 mg nivolumab will be similar to that of 3 mg/kg nivolumab.

Nivolumab has been evaluated in a phase II randomized trial at dose cohorts of 0.3mg/kg, 3mg/kg and 10mg/kg [13]. No differences were noted in safety and efficacy between each of these dose levels. BMS has tested and validated a flat dose regimen of 240 mg IV infusion of nivolumab every 2 weeks which is currently approved by FDA. Hence a flat dose is used in the study regardless of patient weight.

Nivolumab pharmacokinetics (PK) and exposures of subjects in these studies have been characterized by population pharmacokinetic (PPK) analysis of data collected these studies, together with PK data from several phase 1, 2, and 3 clinical studies of nivolumab monotherapy in solid tumors. PPK analyses have shown that the PK of nivolumab are linear, with dose proportional exposures over a dose range of 0.1 mg/kg to 10 mg/kg, and are similar across tumor types. Nivolumab clearance and volume of distribution were found to increase with increasing body weight, but the increase was less than proportional, indicating that a mg/kg dose represents an over-adjustment for the effect of body weight on nivolumab PK. Given the relationship between nivolumab PK and body weight, a flat

dose is expected to lead to lower exposures in heavier patients, relative to the exposures in lighter patients.

Using the PPK model, nivolumab steady-state trough, peak and time-averaged concentration (Cminss, Cmaxss, and Cavgss, respectively) were predicted for a flat nivolumab dose of 240 mg Q2W and compared to those following administration of 3 mg/kg Q2W in NSCLC subjects. A dose of 240 mg nivolumab is identical to a dose of 3 mg/kg for subjects weighing 80 kg, which is the approximate median body weight of NSCLC subjects in the 3 Phase 2 and 3 BMS clinical studies of nivolumab monotherapy. The geometric mean values of Cminss, Cmaxss, and Cavgss with flat dosing are slightly (< 15%) higher than that produced by a 3 mg/kg dose, and the coefficient of variation (cv%) in these measures of exposure are only slightly (< 10%) greater than that of 3 mg/kg dosing.

Thus a flat dose of 240 mg every 2 weeks is recommended for investigation in this study.

1.4 Risk Benefit Ratio of Proposed Regimen

The proposed study is specifically addressing an unmet need of treating bladder cancer in patients who are not candidates for chemotherapy. This is a growing subset of population within bladder cancer with increasing incidence in elderly patients with impaired performance status or renal function or associated comorbidities.

Also PD-1 inhibition therapy has demonstrated efficacy in urothelial cancer and nivolumab was recently FDA approved for use in urothelial cancer of bladder. The benefit risk ratio for the proposed study is very favorable as nivolumab is well tolerated and has proven efficacy in urothelial cancer. There is adequate clinical trial data establishing the role of nivolumab in urothelial cancer and the results have led to FDA approval for this indication. There are clinical trials conducted in lung cancer and melanoma evaluating the combination of nivolumab and RT with promising efficacy and established safety.

The standard therapy for patients who cannot tolerate a radical cystectomy procedure for localized/locally advanced bladder cancer is concurrent chemotherapy consisting of either cisplatin and 5FU or 5FU and mitomycin regimen with RT. However at least 40% of patients with bladder cancer are not candidates for chemotherapy but are likely to tolerate immune therapy. This study is proposed in the chemotherapy ineligible patient population for whom palliative care is radiation therapy alone. Adding concurrent nivolumab is likely to have radiosensitizing effect and enhance efficacy outcomes.

The majority of treatment and study procedures are routine therapy for treatment of bladder cancer. Nivolumab is being provided by BMS. The radiation therapy and labs are part of routine care. Scans for staging pre and post therapy are also part of routine care. The bladder surveillance with cystoscopy and biopsy after therapy completion are also considered routine therapy. Study related research procedures such as immune monitoring and correlative studies will be covered by the study funding.

1.5 Study Sites

Karmanos Cancer Institute, Detroit MI will be the coordinating center and will be joined by participating sites to open this trial. There will be about 2-3 other subsites where this study will be open.

1.6 Withdrawals

Subjects may discontinue study treatment or withdraw their consent to participate in the study at any time without prejudice. The investigator may withdraw a subject from study treatment or from the study if, in his or her clinical judgment, it is in the best interest of the subject or if the subject cannot comply with the protocol.

In addition, any of the following conditions require withdrawal of the subject from study treatment:

- An AE or intercurrent illness that in the opinion of the investigator warrants the subject's withdrawal from treatment
- Necessity for treatment with other investigational drug or other anticancer medications prohibited by protocol
- Participation in another clinical study using an investigational agent
- Request by regulatory agencies for termination of treatment of an individual subject or all subjects under this protocol
- Sexually active subjects who refuse to use medically accepted barrier methods of contraception (e.g., male condom, or diaphragm with spermicidal gel) during the course of the study and for 3 months following discontinuation of study treatment.
- Inability to tolerate nivolumab

- Nivolumab treatment delays greater than 6 weeks
- Progressive disease (PD) as determined by the investigator.

The reason for study treatment discontinuation will be documented. For subjects who discontinue or are withdrawn from study treatment, every effort must be made to undertake protocol-specified follow-up procedures and end-of-treatment assessments, if possible, unless consent for follow up in the study is also withdrawn.

If a subject fails to return for the protocol-defined visits, an effort must be made to determine the reason. If the subject cannot be reached by telephone, a registered letter should be sent to the subject (or the subject's legal guardian) requesting contact with the clinic.

If a subject is discontinued from study treatment because of an AE considered to be related to study treatment and the event is ongoing 30 days after the last dose of study treatment, the event must be followed until resolution or determination by the investigator that the event has become stable or irreversible.

If a subject withdraws consent to participate in the study, the reason for withdrawal will be documented, no study procedures or assessments will be performed, and no further study data will be collected for this subject, other than the determination of survival status from public records such as government vital statistics or obituaries.

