2.3 Study Calendar

Prestudy labs, physical exam and EKG should be done within 28 days of day 1. Day 1 labs can be done within 3 days of day 1. A window of +/- 3 days is permitted for the days of nivolumab therapy.

Testing	Pre study	Wk 1	Wk 3	Wk 5	Wk 7	Wk 9	Wk 11	Wk 13	Wks 15,17, 19,21, 23,25	6, 9 and 12 mths ⁴
H and P	X	X	X	X	X	X	X	X	X	X
VS, Wt	X	X	X	X	X	X	X	X	X	X
PS	X	X	X	X	X	X	X	X	X	X
Tox	X	X	X	X	X	X	X	X	X	X
Labs ¹	X	X	X	X	X	X	X	X	X	X
TSH, free T3/T4	X				X			X		X
ECG ²	X									
Cystoscopy ⁷	X							X		X

Biopsy ⁷	X							X		X
CT/MRI ³ of abdomen/pelvis	X							X		X
CXR/ chest CT ³	X									
Nivolumab		X	X	X	X	X	X	X	X	
visits during RT ⁵		X	X	X	X	X				
PFS/OS ⁶		X	X	X	X	X	X	X	X	X
Biomarkers ³	X				X			X		X
QOL questionnaires ³	X	X	X	X	X	X	X	X	X	X

1. Labs include: CBC diff, platelets, Electrolytes, BUN, creatinine, glucose, Albumin, alkaline phosphatase, total bilirubin, calcium, total protein, SGOT, SGPT. Pregnancy test for women of child bearing potential within 7 days of study enrollment and every 6 weeks thereafter.
2. ECG at screening and repeat if clinically indicated.
3. ICF, Baseline biomarkers, QOL questionnaires and all tumor evaluation/measurement scans must be within 42 days prior to treatment. CT/MRI of abdomen and pelvis is required for pretreatment and subsequent tumor assessments. CXR/CT chest is required at screening only to evaluate for metastases. Biomarkers should be collected at time of PD.
4. 6, 9 and 12 month visits will be from start of therapy. A window of +/- 28 days is permitted for these visits.
5. RT will be done **continuously** daily Monday to Friday (except for weekends and holidays) for a total of 32-35 fractions from week 1 to week 8. The time period of 8 weeks is a maximum duration as the radiation fractions can get delayed due to holidays, machine downtime, patient cancellation due to transportation etc. During RT patients should be evaluated for toxicity at a minimum every other week. Nivolumab should be started +/- 3 days of first day of RT.

6. After 12 months the patients will be followed for PFS and OS every 3 months for a maximum of 5 years.

7. Screening cystoscopy and biopsy can be performed within 6 months of day 1. On study cystoscopy will be done at week 13 and at months 6, 9 and 12 +/- 28 days. Biopsies will be required at week 13, month 6 and month 12 +/- 28 days. Month 9 biopsies done if clinically indicated.

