3.0 STUDY POPULATION

3.1 Inclusion Criteria

- 1) Localized urothelial cancer of bladder with presence of transitional cell carcinoma (TCC) component. Mixed histologies are allowed.
- 2) Clinical or pathologic stage T2 –T4 disease including T4a and 4b if feasible to treat with radiation therapy.
- 3) Locoregional lymph node metastases are permitted but patients with distant metastases are ineligible. Imaging to evaluate for distant metastases should consist of a minimum of CT/MRI of abdomen/pelvis or CT urogram and a CXR or CT chest. Patients for which there is clinical suspicion or symptoms of bone metastasis should have a bone scan completed to rule out metastatic disease prior to enrollment on study.
- 4) Agreeable to consider radiation therapy (RT) for the urothelial cancer: patients have to be evaluated by a radiation oncologist and deemed to be candidates for RT.
- 5) The patients must not be candidates for chemotherapy due to at least one of the following reasons:
 - a. Performance status of 2
 - b. Creatinine clearance \leq 60 ml/min as calculated by the Cockcroft-Gault formula.
 - c. Cardiac disease such as NYHA Class III or IV heart failure or cardiac ischemia within the last 12 months, grade 2 or greater neuropathy, or other

comorbidities based on which patient is not considered a candidate for chemotherapy.

- 6) Adequate liver function with alkaline phosphatase, AST and ALT ≤ 3 x upper limit of normal and bilirubin < 1.5 x ULN
- 7) Adequate Bone marrow function defined as absolute neutrophil count $\geq 1500/\text{mm}^3$ and hemoglobin ≥ 9 g/dL and platelets $\geq 100\text{K}/\text{mm}^3$.
- 8) PS of 0-2 by Zubrod score
- 9) Life expectancy of 12 months
- 10) Age ≥ 18 years of age
- 11) Willingness to sign informed consent
- 12) Patients cannot have active autoimmune disease or immunosuppressive conditions.
- 13) Serum creatinine ≤ 1.5 X institutional ULN or creatinine clearance > 40 ml/min as calculated by the Cockcroft-Gault formula.
- 14) In females with childbearing potential, or men with partners of child bearing potential, willingness to use adequate contraception during the treatment period and for a minimum duration of 5 months after last dose of nivolumab.
- 15) Maximal tumor resection has been performed as feasible.

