A *nonserious adverse event* is an AE not classified as serious.

Nonserious Adverse Event Collection and Reporting

The collection of nonserious AE information should begin at initiation of study drug. All nonserious adverse events (not only those deemed to be treatment-related) should be collected continuously during the treatment period and for a minimum of 100 days following the last dose of study treatment.

Nonserious AEs should be followed to resolution or stabilization, or reported as SAEs if they become serious. Follow-up is also required for nonserious AEs that cause interruption or discontinuation of study drug and for those present at the end of study treatment as appropriate.

Laboratory Test Abnormalities

All laboratory test results captured as part of the study should be recorded following institutional procedures. Test results that constitute SAEs should be documented and reported as such.

The following laboratory abnormalities should be documented and reported appropriately:

- any laboratory test result that is clinically significant or meets the definition of an SAE
- any laboratory abnormality that required the subject to have study drug discontinued or interrupted
- any laboratory abnormality that required the subject to receive specific corrective therapy.

Pregnancy

If, following initiation of the investigational product, it is subsequently discovered that a study subject is pregnant or may have been pregnant at the time of investigational product exposure, including during at least 6 halflives after product administration, the investigational product will be permanently discontinued in an appropriate manner (eg, dose tapering if necessary for subject safety).

The investigator must immediately notify Worldwide Safety @BMS of this event via the Pregnancy Surveillance Form in accordance with SAE reporting procedures.

Follow-up information regarding the course of the pregnancy, including perinatal and neonatal outcome and, where applicable, offspring information must be reported on the Pregnancy Surveillance Form [provided upon request from BMS]

Any pregnancy that occurs in a female partner of a male study participant should be reported to BMS. Information on this pregnancy will be collected on the Pregnancy Surveillance Form.

Overdose

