In patients who received nivolumab as a 60-minute intravenous infusion, infusion-related reactions occurred in 6.4% (127/1994) of patients. In a trial assessing the pharmacokinetics and safety of a more rapid infusion, in which patients received nivolumab as a 60-minute intravenous infusion or a 30-minute intravenous infusion, infusion-related reactions occurred in 2.2% (8/368) and 2.7% (10/369) of patients, respectively. Additionally, 0.5% (2/368) and 1.4% (5/369) of patients, respectively, experienced adverse reactions within 48 hours of infusion that led to dose delay, permanent discontinuation or withholding of nivolumab.

Embryo-Fetal Toxicity

•Based on its mechanism of action, OPDIVO can cause fetal harm when administered to a pregnant woman. Advise pregnant women of the potential risk to a fetus. Advise females of reproductive potential to use effective contraception during treatment with a Nivolumab containing regimen and for at least 5 months after the last dose of Nivolumab.

Lactation

•It is not known whether OPDIVO is present in human milk. Because many drugs, including antibodies, are excreted in human milk and because of the potential for serious adverse reactions in nursing infants from Nivolumab -containing regimen, advise women to discontinue breastfeeding during treatment.

Serious Adverse Reactions

•In Checkmate 017 and 057, serious adverse reactions occurred in 46% of patients receiving Nivolumab (n=418). The most frequent serious adverse reactions reported in at least 2% of patients receiving Nivolumab were pneumonia, pulmonary embolism, dyspnea, pyrexia, pleural effusion, pneumonitis, and respiratory failure.

Common Adverse Reactions

•In Checkmate 017 and 057, the most common adverse reactions ($\geq 20\%$) in patients receiving Nivolumab (n=418) were fatigue, musculoskeletal pain, cough, dyspnea, and decreased appetite.

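### The contraception withdrawal rule in Section 1.6 gives 3 months after study treatment, in conflict with the 5-month minimum after the last nivolumab dose in inclusion 14 and Appendix C

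*Combined protocol and SAP*

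**What the plan says.** Three places in the protocol set a contraception period after treatment.

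- **Section 1.6 (Withdrawals).** The list opens by saying that "any of the following conditions require withdrawal of the subject from study treatment". One condition is that a sexually active subject refuses medically accepted barrier contraception "during the course of the study and for 3 months following discontinuation of study treatment".
- **Section 3.1, inclusion 14.** Women of childbearing potential, and men with partners of childbearing potential, must be willing to use adequate contraception during treatment and "for a minimum duration of 5 months after last dose of nivolumab".
- **Appendix C, Embryo-Fetal Toxicity.** The drug can cause fetal harm. Females of reproductive potential are to be advised to use effective contraception during treatment and "for at least 5 months after the last dose of Nivolumab".

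Section 1.6 also has a discretionary route: the investigator may withdraw a subject where, in clinical judgment, "it is in the best interest of the subject or if the subject cannot comply with the protocol". No text explains why the bullet gives a shorter period than the other two places.

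**The concern.** The only mandatory withdrawal rule aimed at contraception carries a shorter period than the protocol's own minimum. A subject who agreed to 5 months at entry, and who later says during treatment that 3 months is the most they will accept, does not meet the condition in the bullet. Action then rests on the investigator's discretion. The trial is planned for a coordinating center and about 2–3 other sites, so staff who counsel from Section 1.6 and staff who counsel from inclusion 14 could give different periods. What is at stake is fetal exposure to a drug that the protocol says can cause harm. No efficacy or safety estimate is affected.

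**Working it through.** The plan gives no computed figure to reproduce. The check sets the texts side by side and does simple date arithmetic, with one month = 365.25/12 = 30.44 days.

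**1. The texts compared**

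| Place | Who | Method | Period after treatment | Counted from |
|---|---|---|---|---|
| Section 1.6 bullet | all sexually active subjects | barrier | 3 months | discontinuation of study treatment |
| Inclusion 14 | women of childbearing potential; men with such partners | adequate | at least 5 months | last nivolumab dose |
| Appendix C | females of reproductive potential | effective | at least 5 months | last nivolumab dose |

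The bullet is wider on population and stricter on method, but shorter on duration. For men, the mismatch is with inclusion 14 alone.

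**2. Gap if the course of the study means the treatment period and nivolumab is given last**

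- 3 × 30.44 = 91.3 days
- 5 × 30.44 = 152.2 days
- Gap: 152.2 − 91.3 = 60.9 days, which is 60.9/152.2 = 40% of the 5-month period

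Nivolumab is normally the last treatment. The study calendar doses it to week 25, while for radiotherapy (RT) "The time period of 8 weeks is a maximum duration" (Section 2.3, footnote 5).

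**3. Same reading, but RT is given last**

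This assumes that study treatment includes RT. The extreme case is one nivolumab dose on day 0, RT started on day 3 (the edge of the ±3-day window) and run for the full 8 weeks, so that the last fraction falls on day 58 or 59.

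- 58 + 91.3 = 149.3, and 152.2 − 149.3 = 2.9 days short
- 59 + 91.3 = 150.3, and 152.2 − 150.3 = 1.9 days short

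On this reading the gap therefore runs from about 2 to 61 days, and the upper end is the usual case.

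**4. Gap if the course of the study includes follow-up**

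- Nivolumab ends by about 6 months: 6 × 30.44 = 182.6 days
- Five months later: 182.6 + 152.2 = 334.8 days
- Earliest 12-month visit, with the ±28-day window: 365.25 − 28 = 337.25 days

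The 5-month period would end before the 12-month visit, and follow-up then continues to a maximum of 5 years. The gap is zero. The clause adding 3 months after treatment would then have nothing to add.

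**5. Other safeguards**

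- *Pregnancy tests.* Section 4.2 asks for tests within 7 days of enrollment, every 6 weeks, and at approximately 30 and 70 days after nivolumab stops. Both post-treatment tests fall before day 91, so neither falls between days 91 and 152. Calendar footnote 1 says every 6 weeks with no end date, but Section 4.2 is the text that specifies testing after discontinuation.
- *Pregnancy rule.* Section 5.5 counts exposure "including during at least 6 halflives after product administration", but it acts only once a pregnancy is discovered. It does not set a contraception period.

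**The case against.** The strongest reply is that the bullet does not set the contraception commitment at all. Inclusion 14 does, and every relevant participant accepts 5 months in order to enroll. The bullet is a trigger for stopping treatment. Once treatment has ended there is nothing to withdraw from, so the rule cannot act in months 3 to 5 whatever number it carries. This stands, and it limits the consequence to a refusal voiced during treatment by someone who earlier agreed to 5 months. Even then, the discretionary clause already lets the investigator act.

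A second reply is that Section 1.6 itself distinguishes study treatment from the study, so its opening phrase could literally cover follow-up. That also stands as a possible reading, and on it the shortfall disappears. It does not rescue the wording, because it leaves the 3-month clause without purpose, and a reader who takes that clause at face value will still arrive at 3 months.

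A third reply is that few people are concerned. Section 1.2 notes that "The median age of incidence of bladder cancer is 73 years" and at most 34 patients are to be enrolled, although anyone aged 18 or over is eligible. This is fair.

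Two stronger readings are tempting. A reader might infer that the protocol lets participants stop contraception at 3 months. It does not: the bullet says when treatment must be stopped, and inclusion 14 remains in force. A reader might also infer that participants are told the wrong period. That cannot be judged, because the consent pages were not available for review.

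**Conclusion.** Wrong as written: a minor safety-wording correction. Section 1.6 states 3 months where inclusion 14 and Appendix C state at least 5, and no text reconciles them.

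The shortfall is up to about 61 days, assuming that the course of the study means the treatment period and that nivolumab is the last treatment given. It falls to about 2–3 days if RT counts as study treatment and outlasts a single nivolumab dose, and to zero if the phrase is taken to include follow-up. A reader might infer that a 2-month gap always exists. The documents do not support that, because the phrase is open to the longer reading.

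The practical effect is small under every reading, and nothing in the sample size, endpoints or analysis depends on it. It is still worth correcting, because it is a safety figure in a mandatory rule and the protocol already states the right period twice.

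**What to change.** Change only the duration in the Section 1.6 bullet, so that it ends: during study treatment and "for at least 5 months after the last dose of Nivolumab". This states the treatment period explicitly, counts from the last nivolumab dose as inclusion 14 and Appendix C do, and removes the doubt about follow-up. Keep the existing barrier-method requirement and the reference to sexually active subjects. Both are stricter than inclusion 14, and the mismatch in duration gives no reason to loosen them. Check that the consent form gives the same 5-month period.

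The cost is one line in an amendment and a check of the consent form.
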